6.2 Safety endpoints

- TEAEs⁷ up to 5 days after study treatment discontinuation
- SAEs up to 30 days after study treatment discontinuation
- AEs leading to premature discontinuation of the double-blind study treatment
- AEs of special interest starting or worsening after the first dose of the first treatment period until EOS (and after adjudication by the ISB):
 - Narcolepsy-like events (e.g., excessive daytime sleepiness, cataplexy)
 - Complex sleep behavior events.
 - Suicidal thoughts and/or behaviors.
- Change from Baseline (mean of the two PSG nights at V2, run-in period) to the Days 1 and 2⁸ of each period in vital signs (systolic and diastolic BP, pulse rate and body temperature)
- Change from Baseline (V1) to the second morning after the PSG nights at V7 in body weight
- Treatment-emergent ECG abnormalities from V3 until EOT
- Change from Baseline (V2, second morning) to the second morning after the PSG nights at V3, V4, V5, V6 and V7 in ECG parameters
- Marked laboratory abnormalities on double-blind study treatment
- Change from Baseline (V2, second morning) to the second morning after the PSG nights at V3, V4, V5, V6 and V7 in laboratory variables
- Change from Baseline (mean of the two PSG nights at V2, run-in period) to Days 1 and 2⁸ of each treatment period in:
 - Digit Symbol Substitution Test (DSST[®]) performed in the morning, 30–60 minutes after lights on
 - Sheehan Disability Scale (SDS[®]) performed in the morning, 30–60 minutes after lights on
 - Karolinska Sleepiness Scale (KSS) performed in the morning, 30–60 minutes after lights on
- Incidence of most severe suicidal ideation and suicidal behaviors according to the C-SSRS[®] for each treatment period.

⁷ A TEAE is any AE temporally associated with the use of study treatment from Day 1 until 5 days after last study drug intake in each treatment period and until 5 days after study treatment discontinuation whether or not considered by the investigator as related to study treatment.

⁸ Days 1 and 2 is the mean of the first and second morning values after the two PSG nights of a treatment period.

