10.2.4 Safety variables

Safety analysis will be conducted on the SS, and will include all safety data collected up to 30 days after study drug discontinuation.

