10.3.5.2 Adverse events

AEs and SAEs in subjects who were screened but not part of the SS will be listed.

The number and percentage of subjects experiencing TEAEs and SAEs will be tabulated by dose and by:

- MedDRA™ system organ class (SOC) in alphabetical order and individual preferred term within each SOC, in descending order of incidence in the highest dose group.

- Frequency of subjects with events coded with the same preferred term, in descending order of incidence in the highest dose group.

TEAEs, AEs of special interest and SAEs will be tabulated as described above by severity and relationship to study treatment. AEs leading to premature discontinuation of the study treatment and AEs with outcome death will be summarized as described above.

AEs and SAEs with onset between screening and first day of double-blind study treatment will also be summarized.

Listings will be provided for all reported AEs, including SAEs. In addition, separate listings will be provided for SAEs, for AEs leading to premature discontinuation of study treatment, and for AEs with outcome death.

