#### **4 GENERAL ANALYSIS CONSIDERATIONS**

Unless noted otherwise, all statistical summaries will be presented by dose group and in the following order: Placebo, ACT-541468 5 mg, ACT-541468 10 mg, ACT-541468 25 mg, ACT-541468 50 mg.

Categorical data will be summarized by frequency counts and percentages. Unless specified otherwise, percentages will be based on the total number of subjects in the corresponding dose group.

Continuous data will be summarized using descriptive statistics (N, mean, standard deviation, median, minimum and maximum).

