### 10.1 Adverse events

Adverse events (AEs) will be coded using MedDRA. The MedDRA version used for reporting will be specified in the footnote of the applicable output.

AEs will be assigned to the dose group based on the AE start date. AEs with an incomplete or missing start date will not be assigned to a treatment period.

Treatment-emergent AEs are those that occurred from the start of the treatment period [see Section 13.1] until 5 days after last study treatment intake in each treatment period (or until the start of the next treatment period, if earlier).

Non-treatment emergent AEs are those that occurred before the first treatment period or more than 5 days after the last study treatment intake of a given treatment period until the start of the next treatment period, or until the end of the last treatment period [see Section 13.2].

Post-treatment emergent AEs are those that occurred after the end of the last treatment period [see Section 13.2].

AEs will be summarized (frequency counts and percentages) by SOC and/or PT, and maximum intensity. AEs occurring during the run-in single-blind placebo treatment period will also be included in AE summaries defined below (except for AEs leading to premature discontinuation or temporary interruption, or on-treatment deaths).

Deaths (whether on-treatment or not), and AEs (whether treatment-emergent or not) leading to premature study treatment discontinuation or temporary interruption will be assigned to the dose group (including single-blind placebo) of the last dose taken before death or onset of AE, respectively.

The following AE summaries will be provided:

- Treatment-emergent AEs,

- Treatment- and non-treatment emergent AEs,
- Post-treatment emergent AEs,
- Treatment-emergent AEs related to study treatment,
- Treatment- and non-treatment emergent AEs related to study treatment,
- AEs leading to premature discontinuation of double-blind study treatment,
- AEs leading to temporary interruption of double-blind study treatment,
- Occurrence of treatment and non-treatment emergent non-serious AEs,
- Treatment-emergent serious AEs (SAEs),
- Treatment- and non-treatment emergent SAEs,
- Occurrence of treatment- and non-treatment emergent SAEs,
- Treatment-emergent SAEs related to study treatment,
- Treatment- and non-treatment emergent SAEs related to study treatment,
- Treatment- and non-treatment emergent AEs with fatal outcome,

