### **13.2 Treatment period**

A treatment period is defined as the time from the start of the treatment period [see Section 13.1] until the start of the next treatment period. The end of the last treatment period (e.g., the fifth treatment period or an earlier treatment period if subject prematurely discontinued) is the date of first safety follow-up telephone call, or 12 days after the last study treatment intake, whichever is earlier.

After the single-blind placebo treatment period, subjects are to receive one of 5 study treatments in each of the 5 double-blind treatment periods in order of the sequence they are randomized to.

These treatment periods are used to assign assessments/events to dose groups (including single-blind placebo).

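### SAP 10.1 provides no table of the protocol's SAE endpoint to day 30, no general relatedness table for late SAEs, and no column rule for post-treatment events

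*SAP*

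**What the plan says.** **Protocol.** Section 6.2 lists as an endpoint "SAEs up to 30 days after study treatment discontinuation". Section 10.2.4 says the safety analysis "will include all safety data collected up to 30 days after study drug discontinuation". Section 10.3.5.2 states: "The number and percentage of subjects experiencing TEAEs and SAEs will be tabulated by dose", and adds a breakdown by severity and by relationship. Section 9.2.2 collects SAEs over the same 30 days, whereas section 9.1.4 records AEs in general only to day 5. The endpoint for adverse events of special interest (AESIs) in section 6.2 runs to end of study (EOS).

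**SAP.** Section 10.1 sorts AEs into three classes: treatment-emergent (to day 5 after the last intake of a period), non-treatment emergent (up to the end of the last treatment period), and a third class: "Post-treatment emergent AEs are those that occurred after the end of the last treatment period". Section 13.2 fixes that end point: it "is the date of first safety follow-up telephone call, or 12 days after the last study treatment intake, whichever is earlier". The five SAE summaries use the first class alone or the first two together; one of the widest is "Treatment- and non-treatment emergent SAEs related to study treatment". The third class has a single summary, covering all AEs. On columns, section 4 says: "Unless noted otherwise, all statistical summaries will be presented by dose group". Section 13.2 says of the treatment periods: "These treatment periods are used to assign assessments/events to dose groups". Section 12.1 declares one change from the protocol, the analysis set for secondary and exploratory efficacy.

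**The concern.** The protocol promises a tabulated endpoint to day 30, and the SAP's SAE tables stop well before that. If the SAP is followed as written, the number of subjects with an SAE to day 30, overall or judged related, has to be rebuilt from listings. The post-treatment summary does not fill the gap. It has no serious or related version, and its events fall outside every treatment period, so the rule that assigns events to dose groups does not reach them. Nothing records this as a deliberate departure.

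A smaller mismatch sits beside it. The SAP assigns AEs by start date. Protocol 10.2.4.1 and 10.3.5 work from date and time of dosing, and dosing is in the evening. An AE that begins earlier on a first dosing date is therefore counted under a dose not yet taken.

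**Working it through.** **1. Timeline check against the plan's own figures.**
- Treatment phase: 5×2 + 4×5 = 30 days, and 5×2 + 4×12 = 58 days. Protocol 3.1.2 gives 30 to 58.
- Participation: 14 + 30 + 30 = 74 days, and 28 + 58 + 30 = 116 days. Protocol 3.1.2 gives 74 to 116.

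Both reproduce.

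**2. Days left out.** Inputs: endpoint window 30 days (Protocol 6.2); first call on day 5 to 12 after the last intake (Protocol 7.1); period end = min(call day, 12) (SAP 13.2). Days left out = 30 − min(call day, 12).

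| First call | Period ends | Days left out | Share of 30 days |
|---|---|---|---|
| day 5 | day 5 | 25 | 83% |
| day 8 | day 8 | 22 | 73% |
| day 12 | day 12 | 18 | 60% |

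The figures are approximate. Protocol 3.1.1.2 times the call from end of treatment (the morning after the last intake), which can move the count by about a day.

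**3. The five SAE summaries in SAP 10.1.**

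| Classes included | Number | Of which related only | Reaches day 30? |
|---|---|---|---|
| treatment-emergent | 2 | 1 | no: ends day 5 |
| treatment- plus non-treatment emergent | 3 | 1 | no: ends day 5 to 12 |

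None of the five includes the post-treatment class. The two AESI summaries use the second row's classes and end at the same point.

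**4. Where a late SAE goes.** Take an SAE on day 20 after the last dose.
- Non-fatal: it enters the post-treatment AE summary (by system organ class and/or preferred term, and maximum intensity) and the listings. No table shows its relatedness, and no rule gives it a dose column.
- Fatal: it also enters the deaths table, under the last dose taken. The fatal-outcome AE tables, including the related one, stop at the end of the last period.

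A narrow exception exists. AEs leading to discontinuation or interruption are tabulated whether treatment-emergent or not, under the last dose taken. The next dosing date can fall 13 days after the previous intake (step 6). An SAE on that day that stops treatment before dosing lies past the 12-day cap, yet enters the discontinuation table.

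**5. Why the tables cannot be added.** A subject with an SAE on day 3 and another on day 20 appears once in the SAE table and once in the post-treatment summary. The sum is 2; the number of subjects is 1.

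**6. The date rule.** With a full washout of 5 to 12 days, the cycle is 2+5 = 7 to 2+12 = 14 days. First intake is day 1 and last intake day 2; the next first intake is day 8 to 15, which is 6 to 13 days after the previous intake. That is beyond the previous dose's 5-day window. At V4 to V7, a new AE that starts before intake on the first dosing date is therefore not treatment-emergent under Protocol 10.2.4.1, but becomes so for the new dose under SAP 10.1 and 13.1.

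**The case against.** The case for leaving this alone has weight. Late SAEs are summarised and listed, and because AEs in general are recorded only to day 5, the post-treatment summary should hold almost nothing but SAEs. The investigator judges relatedness for every event, so the information exists. About 50 subjects are planned. With the 9.9 h half-life in Protocol 3.2, the uncovered tail starts about 12 half-lives (120/9.9) to 29 half-lives (288/9.9) after the last intake. Keeping such events out of the dose columns is defensible in a crossover. The rule in Protocol 10.3.5, which runs from dosing until just before the next dose, could also be read as leaving them with the last dose. Counting a subject in more than one column already happens in by-dose tables, and the protocol does not ask for one unduplicated total.

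Most of this stands and limits the consequence. It does not supply the tabulation by relationship that the protocol specifies, and a listing is not a table. Two column rules are possible and the SAP adopts neither.

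On AESIs, part of the gap is the protocol's own: it sets an endpoint to EOS but stops recording non-serious AEs at day 5.

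On the date rule, Protocol 6.2 (footnote) and 9.1.1 count from Day 1, so the SAP departs from only one of two inconsistent protocol definitions. A reader might infer that the SAP contradicts itself, because SAP 10.2 treats the first-evening blood sample as a pre-dose baseline. That is not shown: the baseline rule and the AE rule govern different data, and a clash needs an assumed onset dating that the documents do not state.

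**Conclusion.** The point holds. The protocol's SAE endpoint to day 30 is not produced by any table in SAP 10.1. All five SAE summaries omit at least about 18 to 25 of the 30 post-dose days, and SAP 12.1 is silent. Relatedness of late SAEs is not tabulated in general, and the post-treatment summary has no defined columns.

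Two stronger readings should be resisted. One is that late SAEs go unreported, or can appear in only one summary. They appear in the post-treatment summary and the listings; fatal ones are in the deaths table, and a rare one that stops treatment can be in the discontinuation table. The other is that 60 to 83% of SAEs are missed. Those percentages are of days; the documents give no event rate.

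The consequence is modest but the departure is from a pre-specified endpoint, so it should be corrected. The date rule is minor: it applies alike to placebo and every dose, and no bias for or against a dose is shown. The day counts assume the first call is made within its planned window.

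**What to change.** 1. Add one SAE table, all and related, from first double-blind dose to day 30 after discontinuation, with events after the last treatment period in a separate post-treatment column.
2. State the same column rule for the existing post-treatment AE summary. The deaths summary needs no change.
3. Include serious AESIs to EOS in both AESI tables, and reconcile the AESI endpoint with the 5-day AE recording limit.
4. Where AE onset time is captured, assign same-day AEs by time against the intake time that Protocol 5.1.2 already records. Reconcile the date/time definition in Protocol 10.2.4.1 and 10.3.5 with the Day 1 wording in 6.2 and 9.1.1. Where onset time is not captured, the SAP's date rule stands; the documents do not show which case applies.
5. Declare any remaining departure in SAP 12.1.

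The cost is small: one new table, two extended tables and a few sentences in the SAP. SAEs are already collected to day 30, so no new data are needed. The AESI recording limit and the two treatment-emergent definitions need a protocol clarification.

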**Table 2 Imputation rules for an incomplete or missing AE date**

Field	Incomplete date	Missing date
AE resolution date	The upper limit.	No imputation; the AE is considered as ongoing.
AE onset date	No imputation.	No imputation.

## 10.2 Laboratory data

Laboratory analyses are based on data received from the central laboratory. Unless noted otherwise, laboratory data will be converted into SI units, and summaries and listings will include unscheduled assessments.

Descriptive summary statistics of the observed values and absolute changes from baseline to the morning after the second PSG night (scheduled visit) in both hematology and blood chemistry laboratory parameters will be provided. Only scheduled assessments will be considered for this summary.

Baseline is the scheduled assessment performed on the evening of the first PSG night. This assessment is planned immediately prior to treatment intake and is the baseline value for the dose group that immediately follows the assessment. Subjects missing baseline data on a particular parameter will have a missing baseline (and change from baseline) for that parameter.

Descriptive summary statistics of the observed values and absolute changes from baseline [as per definition in Section 13.4] to the last value in the study in hematology and blood chemistry laboratory parameters will be provided, and presented as one group (i.e., All subjects).

Marked laboratory abnormalities are defined in Table 3 below. A marked laboratory abnormality will be assigned to the dose group where it is present regardless of its presence in previous treatment periods.

The number (%) of subjects with marked laboratory abnormalities will be tabulated. A subject will be counted only once, but may be reported in more than one marked laboratory abnormality criterion of a given parameter. Percentages will be based on the number of subjects at risk: those not meeting the criterion at baseline (or having a missing baseline value) and having at least one post-baseline value for a given parameter and treatment period.

All laboratory data for subjects with at least one marked laboratory abnormality will be listed.

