3 OVERALL STUDY DESIGN AND PLAN

3.1 Study design

This is a multi-center, double-blind, randomized, placebo-controlled, five-period, five-treatment crossover, PSG dose-response Phase 2 study in elderly subjects with insomnia disorder.

In order to have approximately 50 subjects randomized, approximately 120 subjects will be screened (estimated screen failure rate is up to 60%). Subjects will be randomized 1:1:1:1:1 to five different sequences of five study treatments according to a Latin square design [see [Table 1](#)]. The five study treatments are oral fixed doses of AC-541468 5 mg (D1), 10 mg (D2), 25 mg (D3) and 50 mg (D4), and placebo (P).

Table 1 Latin square design sequences

		Periods				
		1	2	3	4	5
Sequence	1	Dose 4	Dose 2	Dose 3	Dose 1	Placebo
	2	Dose 2	Placebo	Dose 4	Dose 3	Dose 1
	3	Dose 3	Dose 1	Dose 2	Placebo	Dose 4
	4	Placebo	Dose 4	Dose 1	Dose 2	Dose 3
	5	Dose 1	Dose 3	Placebo	Dose 4	Dose 2

The study will be conducted in approximately 10 sites in two countries (US and Germany).

Subjects who prematurely discontinue the study will not be replaced. Estimated dropout rate for the study is around 10%.

No interim analysis is planned during the conduct of the study. Subjects who complete the study or prematurely discontinue the study will be treated with standard of care according to investigator's opinion.

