10.2.4.2 Laboratory data

Laboratory analyses are based on data received from the central laboratory. All transferred central laboratory data are taken into account regardless of whether they correspond to scheduled or unscheduled assessments. Baseline laboratory test refers to the latest laboratory test performed prior to start of double-blind study treatment.

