10.3.5 Analysis of the safety variables

All safety analyses will be performed on the SS, by dose, using descriptive statistics. All safety data will be listed, with flags for quantitative abnormalities.

Observations and assessments (e.g., AEs, laboratory data) occurring within a treatment period (from the time of dosing to the time immediately prior to the next dose) will be assigned to the dose taken in that period.

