Elevated liver parameters during double-blind treatment will be summarized: the number (%) of subjects meeting the criteria defined below within a given central laboratory sample will be tabulated by dose group. Percentages will be based on the number of subjects at risk: those not meeting the criterion at baseline (or having a missing baseline value) and having at least one post-baseline value for a given parameter and treatment period.

- Aspartate aminotransferase (AST) or alanine aminotransferase (ALT) > 3 × upper limit of normal (ULN)
- AST or ALT > 5 × ULN
- AST or ALT > 10 × ULN
- TBIL > 1.5 × ULN and 2 × ULN
- Alkaline phosphatase > 1.5 × ULN
- (ALT or AST > 3 × ULN) and (TBIL > 2 × ULN)

All AST and ALT values for subjects with an AST or ALT > 3 × ULN will be listed.

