## **13 GENERAL DEFINITIONS AND DERIVATIONS**

### **13.1 Treatment start and end dates**

Double-blind study treatment start and end dates are the earliest and latest dates, respectively, of dose intake recorded on the ‘Study Double-blind Treatment Log’ page.

Run-in single-blind placebo treatment start date (i.e., the start date of the single-blind placebo treatment period), is the earliest date of dose intake (i.e., date of capsules administered) recorded on the ‘Study Single Blind Treatment Dispensing & Accountability’ page at V2.

Treatment period 1 start date is the earliest date of dose intake (i.e., date of capsules administered) recorded for Visit 3 on the ‘Study Double Blind Treatment Dispensing & Accountability’ page.

Treatment period 2 start date is the earliest date of dose intake (i.e., date of capsules administered) recorded for Visit 4 on the ‘Study Double Blind Treatment Dispensing & Accountability’ page.

Treatment period 3 start date is the earliest date of dose intake (i.e., date of capsules administered) recorded for Visit 5 on the ‘Study Double Blind Treatment Dispensing & Accountability’ page.

Treatment period 4 start date is the earliest date of dose intake (i.e., date of capsules administered) recorded for Visit 6 on the ‘Study Double Blind Treatment Dispensing & Accountability’ page.

Treatment period 5 start date is the earliest date of dose intake (i.e., date of capsules administered) recorded for Visit 7 on the ‘Study Double Blind Treatment Dispensing & Accountability’ page.

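### In the by-dose liver and marked-abnormality tables, an elevation first seen on the pre-dose draw at V4 to V7 is counted under no dose when the SAP is applied by date.

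*SAP*

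**What the plan says.** **Draws.** Protocol 7.2 schedules hematology and chemistry on the first evening of V3 to V7, before intake, and on the second morning. Protocol 7.1 puts each of these visits 5 to 12 days after the one before.

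**Baseline.** SAP 10.2 says of the first-evening sample: "This assessment is planned immediately prior to treatment intake and is the baseline value for the dose group that immediately follows the assessment". Protocol 10.2.4.2 has one baseline for the whole double-blind phase: "Baseline laboratory test refers to the latest laboratory test performed prior to start of double-blind study treatment".

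**Denominator.** The marked-abnormality and elevated-liver tables use the same rule: "Percentages will be based on the number of subjects at risk: those not meeting the criterion at baseline (or having a missing baseline value"), provided there is at least one post-baseline value for that parameter and period. For marked abnormalities SAP 10.2 adds: "A marked laboratory abnormality will be assigned to the dose group where it is present regardless of its presence in previous treatment periods".

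**Assignment to dose.** SAP 13.1 sets period starts by calendar date, for example "Treatment period 2 start date is the earliest date of dose intake" at Visit 4. SAP 13.2 runs each period to the start of the next and says: "These treatment periods are used to assign assessments/events to dose groups". Protocol 10.3.5, which names laboratory data, works by time: observations in a period "from the time of dosing to the time immediately prior to the next dose) will be assigned to the dose taken in that period".

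**Declared changes.** SAP 12.1 lists only the move from mFAS to FAS for secondary and exploratory efficacy. SAP 12.3 lists no clarifications.

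**The concern.** Each treatment period has two scheduled draws. The second-morning draw shows what happened over two nights of dosing. Anything that develops later, in the washout, can be seen on a scheduled sample only at the next visit's pre-dose draw. The SAP uses that sample solely to describe the subject's state before the next dose.

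Two rules then work together. By date, the draw lies on the first day of the next period, so it is not a post-baseline value of the dose just taken. As the next period's baseline, an elevated value takes the subject out of that dose's at-risk set. The event can drop out of both columns.

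Protocol 1.3.1 bases the future dose on WASO and safety data. Protocol 1.4.2 names liver and laboratory monitoring at each visit as a risk-minimization measure. These two tables are the planned by-dose counts of laboratory and liver abnormalities, so they should not lose the events that only this draw can detect.

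**Working it through.** The plan states no figure for this point, so there is none to reproduce. The check applies the stated rules to every possible pattern of a single rise.

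**Inputs**
- Draw order per subject: E1 M1 E2 M2 E3 M3 E4 M4 E5 M5, where E is first evening pre-dose and M is second morning (protocol 7.2).
- Sequences (protocol Table 1): "Subjects will be randomized 1:1:1:1:1 to five different sequences of five study treatments according to a Latin square design". They are 50-10-25-5-P; 10-P-50-25-5; 25-5-10-P-50; P-50-5-10-25; 5-25-P-50-10.
- 10 subjects per sequence (protocol 10.5), with full completion assumed.
- One unbroken rise in one criterion per subject.

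**Step 1: patterns.** A rise that begins in a washout is first seen on E2, E3, E4 or E5 and can end at any later draw: 8 + 6 + 4 + 2 = 20 patterns. A rise first seen on a morning draw, M1 to M5, gives 9 + 7 + 5 + 3 + 1 = 25. These are logical cases, not probabilities.

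**Step 2: ordinary date-based reading.** For period k, at risk means Ek does not meet the criterion; counted means at risk and a post-baseline value in period k meets it. If the rise starts on Ek, then:
- period k-1 has only M(k-1), which is normal, so it is not counted;
- period k has an elevated baseline, so the subject is not at risk and an elevated Mk is not counted either;
- in any later period, the rise has ended or the baseline is again elevated, so it is not counted.

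Result: no dose in 20 of 20.

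**Step 3: all eight date-based readings** (preceding dose / later dose only / no dose, out of 20)

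| At-risk baseline | Numerator limited to at-risk | Only later draws counted | Pre-dose draw also counted in its date period |
|---|---|---|---|
| Per period (SAP 10.2) | yes | 0/0/20 | 0/0/20 |
| Per period (SAP 10.2) | no | 0/16/4 | 0/20/0 |
| SAP 13.4 default | yes | 0/16/4 | 0/20/0 |
| SAP 13.4 default | no | 0/16/4 | 0/20/0 |

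No date-based reading credits the preceding dose. Clock time is not among these readings.

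**Step 4: where the draws fall.** Pre-dose draws at V4 to V7: 4 × 50 = 200. Each treatment is last in exactly one sequence, so 4 × 10 = 40 draws follow each treatment. After placebo the next dose is 50 mg in sequences 2, 3, 4 and 5, and nothing follows it in sequence 1. After 50 mg the next dose is 10 mg (sequences 1 and 5: 20 draws), 25 mg (sequence 2: 10) or 5 mg (sequence 4: 10). It is never placebo.

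**Step 5: example.** Suppose two rises are first seen in the washout after 50 mg, one in sequence 1 and one in sequence 5 (Clopper-Pearson 95% CI).
- Protocol 10.3.5 attribution: 50 mg 2/50 = 4.0% (0.5 to 13.7).
- SAP, ordinary reading: 50 mg 0/50 (0 to 7.1) and 10 mg 0/48 (0 to 7.4).

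If a fraction q of subjects had a rise in the washout after 50 mg, the expected number lost from that column is 40q: 0.8, 2.0 and 4.0 at q = 2%, 5% and 10%. These values of q are assumed; the documents give none.

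**Step 6: the remedy under the same test.** Assign by clock time, keep the per-period baseline, let E(k+1) count as post-baseline for dose k, and restrict the numerator to those at risk. Each pattern is then counted once, under the dose after which it began: 20/20 and 25/25, so 45/45. Clock time with one baseline for all periods would instead count 16/20 and 16/25, so 32 of 45, under more than one dose.

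**The case against.** **The date-only rule is an inference.** SAP 13.2 runs each period up to the next one, protocol 10.3.5 works by time, SAP 12.1 does not withdraw it, and intake time is recorded (protocol 5.1.2). Read together, the draw could belong to the preceding dose and also be the next dose's baseline. This is fair: clock-time assignment would resolve the problem, and Step 3 excludes it by construction. But the SAP never states it. SAP 13.1 uses dates, 13.4 takes values on the day of first dose as baseline, and 10.1 assigns adverse events by start date.

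**The draw is late and off drug.** With a 30-day treatment phase (5 × 2 + 4 × 5), it comes about 6 days after last intake: 144 h / 9.9 h = 14.5 half-lives, outside the 5-day TEAE window. The timing is correct, but it does not justify dropping the value. The protocol 10.3.5 window and the SAP 13.2 period both include the washout. A fresh baseline per crossover period is defensible, and the fix keeps it.

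**Few events, and they stay visible.** Entry excludes ALT or AST above 2 × ULN and each exposure is two nights. Subjects with a marked abnormality, or ALT/AST above 3 × ULN, are listed. Unscheduled tests on earlier washout dates go to the preceding dose. Discontinuation reasons, and adverse events leading to discontinuation, follow the last dose taken (SAP 6.2, 10.1). All of this stands and limits the consequence, but none of it corrects the by-dose counts.

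**A stronger reading to avoid.** Because 50 mg always follows placebo when a period follows it, a reader might infer that placebo washout events are moved into the 50 mg column. The documents do not establish that. It needs either a numerator containing subjects outside the denominator, to which SAP 10.2's sentence on assigning abnormalities where present lends some support for one table, or the SAP 13.4 baseline. That default yields to a section-specific definition, and SAP 10.2 has one, citing 13.4 only for the all-subjects summary. On the ordinary reading a rise after placebo only lowers the 50 mg denominator.

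**Conclusion.** The point holds as a loss of events, not as a transfer between doses. Applied by date, with the SAP 10.2 baseline and the numerator inside the at-risk set, an elevation first seen on a V4 to V7 pre-dose draw is counted under no dose (20 of 20 patterns). About 40 draws per treatment are exposed to this with full completion, and fewer with the planned dropout of around 10%.

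The conclusion rests on three assumptions: date-level assignment, the per-period baseline governing the at-risk rule, and a numerator restricted to at-risk subjects. Relaxing either of the last two can put the rise under the next dose, but never under the preceding one. Relaxing the first can restore it to the preceding dose.

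The loss departs from protocol 10.3.5, and the per-period baseline departs from protocol 10.2.4.2. SAP 12.1 declares neither.

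The practical size is probably small. No event rate is given, few events are expected, the intervals in the example overlap, and no dose decision is shown to change. Efficacy analyses, alpha and power are untouched. It is still worth correcting, because the affected tables are the planned by-dose laboratory and liver counts and the correction is cheap.

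**What to change.** In SAP 10.2, for the marked-abnormality and elevated-liver tables:

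1. Assign draws on a dosing date by clock time relative to intake. If a draw time is missing, use the scheduled label, since protocol 7.2 places the first-evening draw before intake.
2. Count the V4 to V7 pre-dose draw as a post-baseline value of the preceding dose as well as the baseline of the next dose.
3. State that the numerator is restricted to the same at-risk subjects as the denominator.

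In SAP 12.1, list the per-period laboratory baseline as a change from protocol 10.2.4.2.

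The cost is three sentences in SAP 10.2, one entry in SAP 12.1 and minor programming, with no new data, visits or subjects. The downside is small: values from about 6 days or more after last intake, outside the 5-day TEAE window, are counted under the preceding dose, as protocol 10.3.5 already provides. The dose given last in each sequence still has no scheduled draw after its second morning. This affects about 10 subjects per treatment and is equal across treatments. A single baseline for all five doses is not recommended, because it would count a persistent rise under several doses.
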